The graph on the left shows that for all values of K we will require more than 34 clusters per arm to detect an effect of 30%. A 33% reduction in the number of girls not transitioning from 7-8th standard will be detectable 80% of the time when K is less than 0.2. For all values of K up to 0.3 34 clusters per arm will be sufficient to detect an effect of 35%.

The graph on the right shows that for values of K above 0.1 the study will require more than 34 clusters to detect a risk ratio of 20% in the retention to 10th standard outcome. A 23% reduction will be detectable 80% of the time when K is less than 0.2. For values of K up to 0.27 the study with 34 clusters per arm will be able to detect a risk ratio of 25% with 80% power.

Married <15yrs

Sex intercourse <15yrs

[figure not shown]

The graph on the left shows that for all values of K more than 0.13 we will require more than 34 clusters per arm to detect an effect on age of marriage of 25%. A 30% reduction in the proportion of girls married before 15 will be detectable 80% of the time when K is less than 0.3.

The graph on the right shows that for values of K below 0.26 the study will require fewer than 34 clusters to detect a risk ratio of 25% in the proportion having sexual intercourse before aged 15.

Cluster size – loss to follow-up and refusal

We show here how the sample size is affected by a reduction in the number of girls in each cluster. These analyses are shown to give a ‘lower bound’ for acceptable levels of loss to follow-up. These are calculated with a risk difference of 35% for transitioning and 23% for retention to 10th standard.

The graph on the top-left shows that between 22 and 27 girls per cluster will be required to be followed up to ensure that there is 80% power to detect a risk ratio of 35% between proportion transitioning from 7th to 8th, depending on the value of K. The graph on the top-right shows that for lower values of K we will require follow-up of an average of at least 22 girls per cluster to detect differences in retention to 10th standard, but that for higher levels of K the requirements for follow-up are more severe. The lower left and lower right graphs show the equivalent calculations for marriage before 15 and sexual intercourse before 15, respectively.

Summary of the sample size calculation results

The study will have 40 clusters per arm.

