There will be 13 girls, on average, enumerated for each of two sequential cohorts in each intervention and control cluster. In effect, 26 girls will be enrolled in each cluster, 1 year apart, corresponding to a total sample of 1050 girls in the control arm and 1050 girls in the intervention arm. We assume that there is minimal loss to follow-up and that 28 girls are followed-up at the endline. With these data we will have 80% power to detect a ratio of around 33% for the transition from 7-8th standard and a 25% ratio for retention until 10th standard. We have included conservative estimates of the control outcome proportions, and reported calculations for a range of K from 0.1 to 0.25.

In order to measure the medium- and short-term outcome indicators for families, the families of the SC/ST adolescent girls recruited in both arms will be interviewed. To facilitate intervention at the family level, each SC/ST adolescent girl in both the arms will be profiled and the main decision maker will be identified. These decision makers will form the sampling frame to recruit the respondents at the family level.

The sample sizes for the girls are summarized in Table 3.

Table 3: Summary of sequential cohort study design

	May 2013	May 2014	February 2017	February 2018
Intervention site, cohort 1	525 girls completed 7 th standard and their families		Follow-up interviews	
Control site, cohort 1	525 girls completed of 7 th standard and their families		Follow-up interviews	
Intervention site, cohort 2		525 girls completed 7 th standard and their families		Follow-up interviews
Control site, cohort 2		525 girls completed 7 th standard and their families		Follow-up interviews

Allocation of clusters to intervention and control arms

68 villages were selected using systematic random sampling from the sample frame of 121.

[figure not shown]
Schools were allocated randomly to either receive the intervention immediately (experimental condition) or at a later date (waitlist control group). The villages were randomised into intervention and control arms so that 34 villages (62 high schools) in intervention and 34 villages (63 high schools) in control arms. This was done by initially selecting 34 villages randomly from the selected 68 villages using STATA 11. These selected 34 villages were allocated into intervention arm and the remaining 34 villages were allocated into control arm.

Accounting for potential contamination

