After allocating the villages to intervention and control arms, there were 12 villages where there was a possibility of contamination because these villages were contiguous with a village in a different arm of the study. To compensate for potential loss of statistical power due to contamination we therefore selected an additional 12 villages (6 intervention and 6 control arm) for inclusion in the study as follows: Of the 53 villages remaining in the sampling frame, we excluded 24 due to their close proximity to villages which had already been selected for the study. From the remaining 29 villages in the sampling frame, an additional 12 villages (6 intervention arm and 6 control arm) with 19 high schools (9 intervention arm and 10 control arm) were randomly selected to be included in the study.

Thus a total of 80 villages (40 in each arm) with 144 high schools (71 intervention arm and 73 control arm) will be included in the study (see diagram below).

Summary diagram

Data collection

In each of the intervention and control villages, quantitative and qualitative assessments will be carried out, both at baseline and following the intervention, among the target groups listed in Table 1.

Closed-ended questionnaires (used in the sequential cohort studies among adolescent girls and their families) have been developed based on a review of available measurement tools. Questionnaires are in Appendix 2. All instruments will initially be developed in English, translated into *Kannada* (the local language), pretested and piloted and revised, and then back-translated. Tables 4, 5 and 6 provide summaries of the different major domains and sub-domains under each indicator that will be measured in these sequential cohort surveys among the adolescent girls and their parents, respectively.

Table 4: Indicator domains and sub-domains that will be measured in sequential cohort studies of SC/ST adolescent girls in control and intervention villages, using a structured behavioural questionnaire

Major domains	Minor domains
Impact and long-term outcomes	
Demographics	Geographic location, school, age, caste, age at menarche, number of siblings in the family (male and female), parents' living status, their education, occupation, land holdings and household income, whether anyone in the family is a Devadasi/sex worker, and relationship to the adolescent girl

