At project completion, we will assess whether, at follow up, there are significant differences between the intervention and control girls in the key indicators of entering 8th standard, completing tenth standard, being married, having sexual debut and entering into sex work. In the course of the analysis we will present simple cluster summaries for the primary outcomes. We will perform statistical tests, using the t-statistic, to assess the significance of and differences observed between the arms.

The final analysis will assess whether the intervention and control schools, adolescent girls and their families significantly differ in terms of the intermediate and short-term outcomes. As recommended by Hayes and Moulton²², given the large number of clusters and because of reasons related to statistical efficiency, individual-level regression methods will be used to test for significant differences in outcomes between intervention and control arms. For each outcome of interest (e.g., the proportion of girls married at the end of the study period, the proportion of girls passing to 10th Standard, etc.), multivariable logistic regression models using generalized estimating equations (GEE)^{23,24} to address clustering at the school level will be estimated. Stata 11 will be used for all analyses. Similar methods will be used to compare short- and medium-term outcomes among SC/ST girls and their families between intervention and control arms.

Qualitative data analysis

The qualitative data will be transcribed and translated into English. Qualitative analysis packages (eg., NVivo9, ATLAS TI) will be used to identify key issues and themes emerging over time. These findings will be used along with the quantitative findings to understand the impact of the intervention.

Addressing confounding factors, selection bias, spill over effect and impact heterogeneity

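### Villages were allocated in two separate 1:1 steps, but the stated t-test on cluster summaries has no term for the step; adding one costs almost nothing, though the gain is probably small

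*Protocol*

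**What the plan says.** Under *Allocation of clusters to intervention and control arms*, 68 villages were drawn from the frame of 121, and 34 of them were picked at random: "These selected 34 villages were allocated into intervention arm and the remaining 34 villages were allocated into control arm". The resulting split was "34 villages (62 high schools) in intervention and 34 villages (63 high schools) in control arms".

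Under *Accounting for potential contamination*, a second step followed once that allocation was known. "Of the 53 villages remaining in the sampling frame, we excluded 24 due to their close proximity to villages which had already been selected" describes how the second pool was formed. From the 29 villages left, the protocol then took "an additional 12 villages (6 intervention arm and 6 control arm) with 19 high schools". The total is confirmed in the sample size summary: "The study will have 40 clusters per arm".

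For the analysis, the sample size section (*Transition from 7-8th Standard*) assumes an unpaired t-test at the end of the trial. *Analysis of primary outcomes* plans simple cluster summaries and adds: "We will perform statistical tests, using the t-statistic, to assess the significance of and differences observed between the arms". It then describes multivariable logistic GEE models that account for clustering by school, with no list of covariates. None of these statements mentions the allocation step.

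**The concern.** The 80 villages are two samples from differently defined pools, each fixed at 1:1. The second pool was restricted to villages farther from those already in the study. The 12 villages flagged as at risk of contamination all belong to the first step. Schools per village also differ somewhat: 125/68 = 1.84 in the first step and 19/12 = 1.58 in the second. A difference in outcome level is therefore possible, though not shown.

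An analysis should normally follow the groups within which the trial was randomised. Because each arm holds the same share of second-step villages (6/40 = 15%), a difference between the steps cancels from the arm comparison. An unblocked t-test still counts it as noise. What is at stake is efficiency: an interval wider than it needs to be and a test that runs below its nominal 5%. The extra villages were added to protect power, so it makes sense not to give part of that back.

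The protocol's own screening may not pick this up. *Assessing baseline balance* relies mainly on how far adjustment moves the treatment effect, and a factor balanced by design moves it by essentially nothing. That section also names a variance criterion, but it does not mention the allocation step.

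**Working it through.** **Inputs from the protocol.** Step 1: 34 + 34 villages. Step 2: 6 + 6 villages, from 53 − 24 = 29. Alpha 5% (taken as two-sided, which reproduces the tables), power 80%, 28 girls per cluster, K from 0.1 to 0.25. Central control proportions: 13% (transition) and 30% (retention). Target reductions: about 33% and 25%. **Assumed:** the difference d in outcome level between the two sets of villages, which is not in the documents and is varied below.

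**1. The protocol's own figure.** The unmatched cluster formula is

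c = 1 + (1.960 + 0.842)² × [p0(1−p0)/n + p1(1−p1)/n + K²(p0² + p1²)] / (p0 − p1)².

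With p0 = 0.17, p1 = 0.119, n = 28 and K = 0.15 / 0.20 / 0.25, it gives 30.4 / 32.7 / 35.6 clusters per arm, exactly as tabulated. With p0 = 0.30 and a 20% reduction it gives 38.8 / 44.4 / 51.7, also as tabulated. The design calculation is therefore that of an unblocked t-test.

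**2. Effect of the two steps on the variance.** Let σ² be the variance of village means within arm and step.

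- True variance of the arm difference: 2σ²/40. The term in d cancels because each arm is 34 + 6.
- Each arm's sum of squares gains (34 × 6/40)d² = 5.1d², so the two arms gain 10.2d².
- Expected pooled variance on 78 df: σ² + (10.2/78)d² = σ² + 0.131d².
- SE relative to its true value: √(1 + 0.131(d/σ)²).

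**3. Size over an assumed range.** SE ratios are from the formula. Error rates are from 100,000 simulated trials per setting.

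| d (SD of village means) | SE ratio, unblocked | Type I error, unblocked | Power, unblocked | Power, arm + step |
|---|---|---|---|---|
| 0 | 1.000 | 0.049 | 0.79 | 0.79 |
| 0.25 | 1.004 | 0.048 | 0.79 | 0.79 |
| 0.5 | 1.016 | 0.047 | 0.78 | 0.79 |
| 1 | 1.063 | 0.037 | 0.75 | 0.79 |
| 1.5 | 1.138 | 0.026 | 0.70 | 0.79 |

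With arm + step, type I error stays at 0.049 to 0.050 throughout.

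**4. On the outcome scale.** Here K of 0.15 to 0.25 is taken within step, and the difference is relative to the mean risk of the two arms.

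- Transition (13%, 33% reduction): SD of village means 0.061 to 0.065. A 25% relative difference between steps (2.7 points) widens the SE by about 1%. A 50% difference (5.4 points) widens it by 4.5 to 5%.
- Retention (30%, 25% reduction): SD 0.092 to 0.106. A 25% difference (6.6 points) widens the SE by 2.5 to 3.3%. A 50% difference (13.1 points) widens it by 9.6 to 12.6%.

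The larger cases strain the protocol's range. A relative difference r adds 0.15 × 0.85 × r² to K². With r = 0.5 and K = 0.25 within step, total K is √(0.0625 + 0.0319) = 0.31, above 0.25. With K = 0.15 within step it is √(0.0225 + 0.0319) = 0.23, inside the range.

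**5. Against planned power.** Step 3 holds the within-step variance fixed. The protocol's K is total between-cluster variation, so it already contains any difference between the steps. A separate simulation held total K fixed, with 40 v 40 villages, 26 girls each, and a quarter of the between-village variance due to the step.

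| Outcome, K | Unblocked | Arm + step |
|---|---|---|
| Transition, 0.20 | 0.835 | 0.842 |
| Transition, 0.25 | 0.816 | 0.829 |
| Retention, 0.20 | 0.911 | 0.922 |
| Retention, 0.25 | 0.876 | 0.895 |

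For transition with no step effect, unblocked power is 0.836 and 0.811. Planned power is therefore kept, and the step term adds about one to two points.

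**The case against.** The strongest reply is that this is detail for a statistical analysis plan. *Analysis of primary outcomes* says only that a t-statistic will be used, and an arm coefficient adjusted for step is also tested with one. The GEE is multivariable with its covariates unlisted, so nothing rules out a step term. Both sets of villages come from one frame under the same eligibility rules, and no passage links proximity to dropout, marriage or sexual debut. Much of this stands. It limits the point to a refinement. It does not remove it, because the one test the protocol describes more fully, in the sample size section, is unpaired and has no such term.

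Three stronger readings are tempting, and the documents do not support them.

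- *The co-primary intervals are too wide.* This holds only if the two sets of villages differ, only in expectation, and only for the t-test. The documents give no difference.
- *The loss could be large*, for example with a 10-point difference at a 13% control rate. Combined with K = 0.2, that implies a total K of √(0.04 + 0.1275 × (0.10/0.13)²) = 0.34, beyond the protocol's upper value of 0.25.
- *The GEE standard errors are too wide as well.* The GEE clusters on school although the village was randomised. Assuming 144/80 = 1.8 schools per village and all clustering at village level, that makes its standard errors about 2 to 10% too narrow, which is the opposite direction.

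**Conclusion.** The point holds in a limited form. The allocation had two separate 1:1 steps, and the stated comparison of cluster summaries does not reflect them. The effect estimate is unbiased, and false positives are not increased. Any cost is lost precision: under 2% of the standard error up to 0.5 SD and about 6% at 1 SD. If there is no difference, nothing is lost. Against the planned power, a realistic gain is one or two percentage points.

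This rests on an assumed difference between the two sets of villages, a two-sided 5% test, and a random 6:6 split. The text says the 12 villages were selected at random but does not spell out how they were divided between arms; the Figure 1 caption says each village was randomly allocated. Severity is low: a free improvement rather than a correction of an invalid analysis.

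**What to change.** In *Analysis of primary outcomes*, state that the arm effect on village summaries will be tested in a linear model with arm and an allocation-step indicator (first 68 villages versus the additional 12). Include the same indicator as a fixed effect in the individual-level regression models. Fix this before outcome data are compared, so that it is not a later choice.

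The cost is one sentence and one degree of freedom (78 to 77; critical t 1.9908 to 1.9913). No new data are needed, since the step for each village is already known.

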SC/ST girls will be enumerated and included in the cohort. We will conduct a complete-capture enumeration of all SC/ST girls in all trial sites, therefore, all SC/ST girls will be approached for inclusion in the trial.

Families

All families of SC/ST girls will be included in the cohort.

Sample size

The sample size calculations are based on the four co-primary outcomes:

1. Percentage of those enumerated in 7th standard (the study cohorts) who ENTER into grade 8th
2. Percentage of those in the study cohorts who complete 10th standard
3. Proportion of girls in the study cohorts who are married at end line.
4. Proportion of girls in the study cohorts who experienced first sexual intercourse at end line

The sample size calculations are based on the parameters shown in the table below. The baseline numbers are found in the KSS Karnataka report for 2010-2011, a rural assessment by KHPT in 2013, the district level household surveys (DLHS) from 2007-2008, and the Integrated Biological and behavioral Assessment (IBBA) conducted by KHPT from 2006-2011. Broadly speaking, the expected effect sizes are guided by the aim of the intervention to bring the outcomes among SC/ST girls in-line with all girls. Therefore, we have used the prevalence of the outcomes in these surveys to estimate plausible effect sizes.

Parameter	Notes
Harmonic mean cluster size	This is based on an enumeration carried out in the 225 high schools located in 121 villages by KHPT. Approximately 15 SC/ST girls are available at each school
Refusal/loss to follow-up	Refusal and loss to follow-up are expected to be low, approximately 5-10% (14 girls per cluster is used in the calculation, multiplied by 2 to account for the two cohorts)
Between cluster variation (k)	The between cluster variation in the outcomes is not known. Therefore, we have reported sample sizes for a range of values.
Control arm proportions	

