1. We have reported a range of Risk Ratio minimum detectable effect sizes from 30-40%. This is considered to be the most likely of the outcomes to be influenced by the intervention
2. We have reported a range of Risk Ratio minimum detectable effect sizes from 20-25%. The lower effect size than for outcome 1 reflects the perception that this will be harder to influence with the intervention as the barriers to staying in school increase over time
3. The intervention will target marriage directly through school and home based interventions. Therefore, we aim to decrease the proportion married before 15 by 25-30%.
4. The intervention will target sexual debut directly through school and home based interventions. Therefore, we aim to decrease the proportion married before 15 by 25-30%.

Type 1 error

We have set this at the 5% level

Power

We have set this at the 80% level

Transition from 7-8th Standard

These and further sample size calculations included estimations of variance of between-cluster differences when an unpaired t-test is used for final analysis, on the basis of calculations provided by Hayes and Betnett¹⁹.

Transition from 7-8th standard is considered to be the most likely of the outcomes to be influenced by the intervention, and we have reported a range of minimum detectable effect sizes, with risk ratio of RR= 0.70-0.60.

The detectable effect sizes of RR=0.70-0.60 is assumed on the basis that the intervention aims to bring down the higher dropout rate among SC/ST girls to be in-line with the state average dropout rates among all girls. The *Sarva Shiksha Abhiyan Karnataka Analytical report 2010-11* (Education in Karnataka 2010-11) documents a dropout rate among SC/ST girls during higher primary grades of 9%, compared to 5.6% among all girls in the state (Table 18A). Therefore, the state average for dropout rates from higher primary grades among all girls is 38% less than the dropout rates of SC/ST girls, corresponding to a risk ratio of RR=0.62. Note that the dropout rates of SC/ST girls in transition from standard 7 to standard 8 are not available from the report at district level disaggregates, so we used the state averages for SC girls and all girls. On the basis of this uncertainty, and the event that the intervention is not able to fully bring SC/ST drop out during transition to the average among all girls, we have sized the trial to detect weaker risk ratio of 0.70 under certain, plausible, conditions.

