The lifeline case study approach provides an opportunity to gain meaningful insight into the lives of participants, and the impact that *Sabala* is having or has had upon their lives. During annual in-depth interviews the girls will engage in participatory lifeline mapping to explore events and experiences in the participants' life before and during the intervention period.

The specific objectives of the case studies are:

- To map changes in individuals and family contexts over time, providing detailed accounts of key events that affect the girls schooling
- To identify common problems faced by girls and how the intervention could (or could not) provide support
- Compare how girls in intervention areas overcome challenges differently from those in the control areas

Thirty girls enrolled in 8th standard at the start of the intervention will be selected and followed for a period of 3 years: 20 girls in the intervention area and 10 girls in control areas. Sampling will be purposive based on Devadasi background, academic performance, and/or socioeconomic status as reported in the baseline questionnaire. If routine tracking data indicates that the girl is at risk of dropout (eg. in case of impending marriage there is a possibility that she leaves the area) the next interviews will be brought forward. In order to gain sufficient in-depth understanding of what leads to dropout and could not be prevented during the Sabala intervention, extra respondents will be recruited purposively among girls who recently dropped out of school in the intervention area: 5 girls in the 2nd year and 5 girls in the 3rd year. This is required as dropout in 8th, 9th and 10th is estimated at about 6% each year.

The lifeline tool will consist of time marked in weeks and months on the x-axis and events, marked on the y-axis according to a five point scale indicating positive or negative perceptions of the event. Different colours and symbols will be used to represent the intervention, school attainment, government schemes such as financial incentives for staying in school, and personal experiences.

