In the 4th year a total of 17 participants will be chosen from the list of policy makers identified at each level. The tool used for data collection will be a semi-structured interview guide. The leads and triggers will be developed around 1) knowledge on the goals, objectives, reach and strategies of the intervention; 2) the level of support in word and action from officials towards these intervention activities; 3) perceptions on applicability of intervention strategies for scale up; and 4) the description of any move by any government body to develop policies and guidelines based on this intervention model for scale.

Probe lists for all in-depth interviews are included in appendix 4

Intervention monitoring

A robust monitoring system will be used to monitor the activities at the school and community level as follows:

- (i) An individual tracking system which tracks individual girls will be developed to monitor inputs, outputs and certain outcome level indicators. The project will facilitate schools to track the girls from marginalized communities during the project period to monitor school achievement and ensure efficient identification of drop-outs, so that the issues related to drop outs can be effectively addressed.
- (ii) Within the communities, project activities such as linkages to the government schemes, school-to-community contact programs, support for tutorials/remedial classes etc. with adolescent girls and their families will be monitored.

[figure not shown]

Figure 1: Allocation of clusters. A total of 80 villages, each randomly allocated into intervention and control arm. Figure 1 illustrates the distribution of control and intervention clusters in the selected districts.

Time period

The total study period will be 4 years: 9 months of start-up activities and baseline assessments, 30 months of intervention, and another 9 months of final assessments and analyses.

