During the start-up period, the baseline data collection instruments and protocols will be developed and finalized, and the data collection teams will be recruited and trained. The following three months will be devoted to baseline data collection. The last 9 months of the project will be devoted to end line data collection (three months), analyses and reporting (six months), and dissemination of the findings to the local communities, to Indian policymakers, and to the international community. Interim analyses will be conducted on a semi-annual basis, and a final report submitted upon completion of the project.

The diagram below shows when key study activities will take place (greyed boxes).

Year		2013		2014				2015				2016				2017				2018	
Quarter		3	4	1	2	3	4	1	2	3	4	1	2	3	4	1	2	3	4	1	2
Quantitative Studies																					
Cohort-1: Intervention & Control site																					
1	Girls																				
2	Family members of girls																				
Cohort-2: Intervention & Control site																					
1	Girls																				
2	Family members of girls																				
3	Principals, teachers and SDMC members																				
Qualitative Studies																					
1	Case studies (1st cohorts of girls from intervention and control, 2 nd and 3 rd cohort drop-outs from intervention)																				
2	IDI with girls, families, teachers, boys (intervention)																				
3	IDI- Champions																				
4	IDI- Policymakers																				
Intervention in intervention clusters																					

Ethical issues

Interviews will be conducted in private settings in a sensitive and non-judgmental manner. Since some of the participants will be minors, we will seek both written informed consent from the girl's parent or legal guardian (if she is unmarried) and informed assent of the girls. We will seek independent informed consent from girls who are married and living with their husband.

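### Two passages end follow-up too early for cohort 2 to complete 10th standard and contradict Table 3; the intervention start relative to cohort 1's entry to 8th standard also needs reconciling

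*Protocol*

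**What the plan says.** **Follow-up and calendar.**
- Protocol, Sampling of the adolescent girls: girls join at the end of 7th standard, cohort 1 in year 1 and cohort 2 in year 2. Follow-up of every girl runs to the beginning of year 4, when most or all are expected to have turned 15.
- Protocol, Time period: a four-year study made up of "9 months of start-up activities and baseline assessments, 30 months of intervention, and another 9 months of final assessments and analyses". The last nine months hold three months of endline collection and six of analysis and reporting.
- Protocol, Table 3: the cohorts have completed 7th standard in May 2013 and May 2014; follow-up interviews are in February 2017 and February 2018.
- Protocol, activity chart under Time period: column headings from quarter 3 of 2013 to quarter 2 of 2018.
- Protocol, Summary: girls are about 13 at entry and are followed to about 16.

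**Exposure and outcome 1.**
- Case studies: "Thirty girls enrolled in 8th standard at the start of the intervention will be selected and followed for a period of 3 years". Sampling of these girls draws on the baseline questionnaire.
- Time period: start-up and baseline come before the intervention ("The following three months will be devoted to baseline data collection").
- The intervention: girls from 7th to 10th standard are among the primary stakeholders.
- Sample size: "14 girls per cluster is used in the calculation, multiplied by 2 to account for the two cohorts". The summary states "With these data we will have 80% power to detect a ratio of around 33% for the transition from 7-8th standard".

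**The concern.** Outcome 2 can be observed only if follow-up lasts until a girl has had time to finish standards 8, 9 and 10. If field staff worked to the sampling section or to the Time period section, cohort 2 would be interviewed while still short of 10th standard. A co-primary outcome would then be missing, by design, in one of two equally sized cohorts. Marriage and sexual debut at endline would also be read at a younger age than Table 3 implies.

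The second question is narrower. Outcome 1 is entry to 8th standard. The sample size pools both cohorts under one effect. If girls in cohort 1 were already in 8th standard when the intervention began, their transition could hardly have been changed by it, and the pooled effect would be diluted. A null result on outcome 1 could then reflect timing and not a failed intervention.

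**Working it through.** **1. Time available to cohort 2.**

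Inputs: cohort 2 joins in year 2, so no earlier than 12 months after the study begins. Table 3 has successive cohorts finishing 7th standard 12 months apart, so I assume one standard per year. Three standards then take about 3 × 12 = 36 months.

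| Source | Endline | Months after cohort 2 joins | Against about 36 |
|---|---|---|---|
| Sampling section | start of year 4 = 36 months in | at most 36 − 12 = 24 | at least 12 short |
| Time period section | months 40-42 | at most 42 − 12 = 30 | at least 6 short |
| Table 3 | February 2018 | May 2014 to February 2018 = 45 | 9 to spare |

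Months 40-42 follow from 9 + 30 = 39 months before the closing phase, then three months of collection before six of analysis (39 + 3 + 6 = 48). Even the last day of a 48-month study is at most 48 − 12 = 36 months after cohort 2 joins, which leaves no time for analysis.

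For cohort 1 the same ceilings are 36 months (sampling section) and 42 months (Time period section), so the shortfall is certain only for cohort 2.

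**2. Overall span.**
- Time period text: 9 + 30 + 9 = 48 months.
- Table 3: May 2013 to February 2018 = 57 months.
- Chart: 2 + 4 + 4 + 4 + 4 + 2 = 20 quarters = 60 months.

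Counted from May 2013, Table 3's endlines fall at 45 months (late in year 4) and 57 months (in year 5). Neither is the beginning of year 4. Age agrees with the longer calendar: 13 + 24/12 = 15, but 13 + 45/12 = 16.75, closer to the Summary's 16.

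**3. Outcome 1: reproducing the protocol's figure.**

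Hayes-Bennett, unmatched, two-sided 5%, 80% power:

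c = 1 + (1.96 + 0.84)² × V / (p0 − p1)², with V = p0(1−p0)/n + p1(1−p1)/n + k²(p0² + p1²).

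Take p0 = 0.13 (the central control value under K and the number of clusters), a 33% reduction (p1 = 0.0871), n = 28 and k = 0.20. Then V = 0.004039 + 0.002840 + 0.000979 = 0.007859 and (p0 − p1)² = 0.001840, so c = 34.5. For k = 0.15 / 0.20 / 0.25 the formula gives 32.7 / 34.5 / 36.9, as in the protocol's table. The 17%, 30% row (30.4 / 32.7 / 35.6) also reproduces.

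**4. Outcome 1: what a smaller cohort 1 effect would do.**

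Power = Φ(|p0 − p1| / √(V/(c−1)) − 1.96), with c = 40 villages per arm, n = 26 girls per village (the enrolment figure in the sample size summary), equal cohorts, and pooled risk ratio (RR) = mean of the two cohort RRs. Cohort 2 is held at RR 0.67. The cohort 1 values of 0.85 and 1.0 are assumptions, not taken from the protocol.

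| Cohort 1 RR | Pooled RR | p1 | Power at k = 0.15 / 0.20 / 0.25 |
|---|---|---|---|
| 0.67 | 0.67 | 0.0871 | 85% / 83% / 81% |
| 0.85 | 0.76 | 0.0988 | 57% / 54% / 52% |
| 1.0 | 0.835 | 0.1086 | 30% / 29% / 27% |

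Example, middle row at k = 0.20: V = 0.008841, standard error √(0.008841/39) = 0.01506, 0.0312/0.01506 = 2.072, and Φ(0.112) = 0.54.

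**The case against.** **On the calendar.** Table 3 carries explicit dates, gives both cohorts ample time, and the chart also runs into 2018. On this view the other two passages are loose wording, and harm follows only if someone prefers them to the dated table. That limits the point: the protocol does contain a workable schedule, and a reader should not infer that outcome 2 will in fact be lost. It does not remove the point, because both passages state when follow-up ends and nothing says that Table 3 takes precedence.

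**On exposure.** A reader might infer that cohort 1 made its transition unexposed and that outcome 1 is therefore underpowered. The documents do not support that.
- The chart is the place where timing is set out ("The diagram below shows when key study activities will take place (greyed boxes"), but its shading is lost in this copy, and the detailed intervention design is a separate appendix. The start date is not legible here, which is not the same as absent.
- Being enrolled in 8th standard at the start also fits a start that coincides with entry to 8th, and late entry could still be influenced.
- 7th standard is named within the intervention's scope.
- The chart entry "Case studies (1st cohorts of girls from intervention and control" does not show that the case-study girls are trial cohort 1. It goes on to a second and third cohort, whereas the trial has two; waves of case-study recruitment are the likelier meaning. The baseline questionnaire is the better link to surveyed girls.
- The protocol gives a range of effects ("we have reported a range of minimum detectable effect sizes, with risk ratio of RR= 0.70-0.60"). With cohort 2 at 0.60 and cohort 1 at 0.80, the pooled RR is 0.70, and the same formula gives 72-77% power at 13% control dropout and 82-88% at 17%, though 57-61% at 9%. The 27-30% figure is a worst case.

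Two further inferences also fail. Table 3's May 2013 cell records girls who have completed 7th standard, not an interview date, so it does not show that the chart opens after the first survey. Reporting the transition effect by cohort may be left to the statistical analysis plan, so its absence here is no fault.

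**Conclusion.** The calendar contradiction stands on legible text and should be fixed. The sampling section allows cohort 2 at most 24 months and the Time period section at most about 30, against about 36 needed for three standards and 45 in Table 3. Followed as written, either would make a co-primary outcome unmeasurable in half the planned sample. This rests on one standard per year and on years counted from the start of the study.

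The outcome 1 point is a query with a conditional consequence. The passages on the case studies, the order of baseline and intervention, and the 7th-standard scope do not settle whether cohort 1 was exposed before its transition. The 80% power statement is arithmetically sound for a pooled reduction of around 33%. It would need restating only if exposure came too late for cohort 1, and the diluted powers illustrate that case under assumed cohort 1 effects.

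**What to change.** 1. Replace the start-of-year-4 end of follow-up in the sampling section, and the 48-month breakdown in the Time period section, with text that agrees with Table 3's endline for each cohort (February 2017 and February 2018). State that both cohorts are followed long enough to observe completion of 10th standard. Check the chart against the same dates, and the school survey, which also uses the beginning of year 4.
2. State in the text when the intervention begins relative to each cohort's entry to 8th standard, and reconcile the case-study, Time period and intervention-scope passages with it.
3. Only if the intervention did not precede cohort 1's entry, restate the outcome 1 power with a reduced cohort 1 effect, giving the assumed values.

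The cost is a few sentences, one corrected calendar and, in the third case, one recalculated power statement that may be less favourable. Relative to Table 3, no extra data are needed.
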